5% using ICSD-II diagnostic criteria. [1] Obstructive sleep apnoea in adolescents is largely unexplored, and the only publication on its prevalence has quite a few methodological flaws, namely small sample size and failure to represent the general population. [5]

It is well documented that childhood / adolescent OSA can lead to a variety of important sequelae which include cardiovascular, growth, neurocognitive and behavioural deficits together with metabolic disturbances. [6-9] Individuals with OSA have higher morbidity, mostly related to respiratory diseases and health care use starting from a young age. [14] They are also found to have poorer quality of life scores than healthy controls. [15] Therefore this proposal deals with an important condition that is currently insufficiently researched.

Two types of childhood OSA

Recent research has emphasized the “newer” type of childhood OSA, namely primarily obese subjects with only mildly enlarged lymphoid tissue. These obese children with OSA present differently and have distinct clinical phenotypic characteristics from non-obese children with OSA. [10] Different metabolic and immunological changes are present in obese children with OSA, and obesity can induce health changes that are independent from an isolated upper airway problem. Therefore the distinction between obese children with OSA from those of normal weight is very crucial. This newer type of childhood OSA is more akin to adulthood OSA as obesity is the major component in both. There is accumulating evidence that this type of childhood OSA begins in adolescence. [16]

Obstructive sleep apnoea in childhood usually remit by adolescence, and a large proportion of adolescents OSA cases are incident cases. Distinct risk factors for OSA are at play at each time point across paediatric ages, underscore the need to separate OSA research for children and adolescents. [16,17]

Why study adolescents?

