Adolescence is a rapid and critical transitional stage of physical and psychological development that generally occurs at the onset of puberty. Major biological changes take place during this period and they include changes to the sex organs, physical parameters, muscle mass, as well as vital developmental changes in brain structure and organization. It is well known that some of these changes will affect various aspects of sleep, predisposing adolescents to the development of OSA. [2-4] This period of growth and maturation is very distinct and should not be seen as a continuum of childhood, and it further emphasizes the importance not to extrapolate childhood OSA information to adolescents.

Research by our research group

We have successfully conducted clinical research on various aspects of childhood OSA. These include determining risk factors and prevalence, [1] establishment of screening methods, [18] examination of neurocognitive, metabolic and cardiovascular complications using cross-sectional and longitudinal study design. [19-27] Our group has also published work on the natural progression of mild OSA and primary snoring in children. [28,29] We have also recently completed a 10-year follow-up study on an OSA cohort and we document that moderate-to-severe OSA in childhood may be associated with higher blood pressure in early adulthood. [30] Thus our proposed study builds on our established track record in childhood OSA research.

(b) Research plan and methodology

Study Subjects

Adolescents will be recruited from local secondary schools which will be randomly selected from the 4 geographic regions of Hong Kong. Inclusion and exclusion criteria are as follows:

Inclusion criteria:

1. adolescents aged 12-16 years.
2. written informed consent from parents and assent from participants available.

Exclusion criteria:

1. subjects who have previously undergone upper airway surgery or currently receiving treatment for OSA.
2. craniofacial anomalies.
3. subjects who are unable to speak or read Chinese.

The study protocol will be submitted to ethic committee of the New Territory East Cluster Board for approval. All subjects will participate on a voluntary basis. The study will be conducted in compliance with the Declaration of Helsinki.

Study Design

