The sample selection will be based on a stratified (by districts) and clustered (subjects within randomly selected schools) randomised sampling frame. We stratify all secondary schools registered under the Education Bureau according to the four geographic regions in Hong Kong (i.e. Hong Kong Island, Kowloon, New Territories East and New Territories West). The student numbers in all secondary schools are available in the Bureau's website. Ten students in each school year grade will be randomly selected from the chosen schools. There are on average 50 children to be recruited per schools therefore we will need to randomly select 15 secondary schools from the whole of Hong Kong. In order to avoid sampling bias towards the region that has less population, the final number of schools to be recruited from each of the four geographical regions would be in proportion to the adolescent population that reside in that region. According to the 2016 population by-census statistics (available from the website of Census & Statistics Department, HKSAR), the proportions of adolescents residing in Hong Kong Island, Kowloon, New Territories East and New Territories West were 16.1%, 30.7%, 25.3% and 27.9% respectively. Thus, this study will recruit proportionally 2, 5, 4 and 4 secondary schools from the 4 regions. This sampling method ensures that our subjects are representative of the local school population. Lastly, this study will recruit and survey the subjects from the four regions in parallel throughout the study period in order to minimise the possible influences of different seasons on study outcomes.

Outcome Measures

- (a) Primary outcome: prevalence of obstructive sleep apnoea as defined by obstructive apnoea hypopnoea index.
- (b) Secondary outcomes: correlation between severity of OSA with clinical, laboratory parameters and cognitive function as measured by Conners' Continuous Performance Test (CPT).

Collection of Data

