The subjects will attend our unit for assessment and explanation of home PSG monitoring. After a 15-minute rest, systolic (SBP) and diastolic (DBP) blood pressure will be taken using the Datascope Accutorr Plus. Two measurements are taken at 1-minute intervals, with a third reading taken 5 minutes later if the difference between the first two >4 mmHg. The average of two repeatable readings (difference ≤ 4 mmHg) will be used. Anthropometric parameters including standing height (in metres) without shoes and body weight (in kilograms) will be recorded using Harpenden Stadiometer (Holtain, UK) and an electronic weighing scale (Tanita BF-522, Japan) respectively according to standard recommendations. [12,32] Waist and hip circumference (in centimetres) will also be obtained. Neck circumference will be measured at the level of the most prominent portion of the thyroid cartilage with the head held erect and the eyes facing forward. Z scores of body mass index and waist circumference will be calculated using local references. [33,34]

If the participating school is agreeable and logistically feasible, our research team can carry out the above at school. However, in our experience schools close to our unit prefer to send their students to us to undergo the various assessments.

All assessments will be carried out during the week to avoid weekday-weekend difference in adolescents' sleep pattern. The students will also complete a chronotype preference questionnaire, result from which can provide guidance regarding effects of sleep phase. The reduced version of Horne and Östberg Morningness–Eveningness Questionnaire (rMEQ) will be used to measure chronotype preference [35]. It consists of five items designed to assess one's preferred bedtime and rise time, the degree of tiredness in the morning, peak time for optimal performance, and self-perceived circadian preference. The rMEQ has been validated in ethnic Chinese individuals, with good psychometric properties [36], and has been used in previous research conducted in adolescents.[37, 38] Participants scored higher than 17 and lower than 12 will be classified as morning-type and evening-type, respectively. Participants with total rMEQ scores between 12 and 17 will be classified as intermediate-type [36].

Sleep study

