The resultant prevalence will be compared to published prevalence of OSA in children. Logistic regression analysis will be used to identify possible risk factors of OSA in adolescents. Potential factors associated with a higher risk of OSA may include male sex, body weight, waist circumference, neck circumference, tonsil size, modified Mallampati score and chronotype. All these factors will be first assessed in univariate analysis. Those found to be significantly associated with OSA in univariate analysis will be assessed in multivariate model. The association between OSA and cardiovascular, metabolic and cognitive outcomes will be investigated. Comparisons will be made between subjects with and without OSA. Linear regression analysis will be conducted to assess the association between these outcomes and OAH. Multiple linear regression analysis will be performed to see if OAH is independently associated with these outcome measures while adjusting for possible confounders such as body mass index. The significant level will be set as $p < 0.05$. All analyses will be performed using SPSS version 20.0.

Feasibility and Timetable of Project

The proposed study will require a total of 30 months (130 weeks) to complete. We will be able to assess 8 subjects per week. For a sample size of 740, we will need 93 weeks for data collection. The first 12 weeks will be used for document preparation and school recruitment. The last 15 weeks will be used for data cleaning and analysis. The remaining 10 weeks should be allowed for clashes with schooling, missed appointments and public holidays.

Education plan

The principal investigator and the collaborator are all experienced teachers and supervisors. This project can further strengthen the educational activities and exchanges of the respective departments. It will also provide a good opportunity to train undergraduate and postgraduate students, especially for someone who is interested in the field of sleep medicine. The student will be provided with the required theoretical and practical training, and will work under close supervision of the principal investigator and related research personnel. This will allow the student to learn the knowledge and skills as a scientist, an ideal opportunity to advance himself / herself.

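### The risk-factor model names body weight but not age in a 12-16-year sample and gives the planned z scores no role, so the weight coefficient mixes adiposity with growth, with a bias of unknown direction

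*Combined protocol and SAP*

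**What the plan says.** Statistical Analysis gives the candidates for the logistic model as an open list, worded as what might be included rather than what will be: "male sex, body weight, waist circumference, neck circumference, tonsil size, modified Mallampati score and chronotype". Each is tested alone, and then: "Those found to be significantly associated with OSA in univariate analysis will be assessed in multivariate model". For the cardiovascular, metabolic and cognitive outcomes, multiple linear regression on the obstructive apnoea hypopnoea index (OAHI) is planned, "adjusting for possible confounders such as body mass index". Age is named in neither place.

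Collection of Data states: "Z scores of body mass index and waist circumference will be calculated using local references". No z score is planned for body weight or neck circumference, and Statistical Analysis does not mention z scores at all.

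The inclusion criterion is "adolescents aged 12-16 years". Under Sampling Frame, "Ten students in each school year grade will be randomly selected from the chosen schools", at an average of 50 per school, which implies five grades in equal numbers. Key Issues names somatic growth among the changes that can affect the upper airway. The background section on the two types of childhood OSA treats obesity as central and adds: "Distinct risk factors for OSA are at play at each time point across paediatric ages".

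**The concern.** Body weight rises with age and height through these years. In a sample drawn evenly across grades, part of the spread in weight is simply age. A logistic coefficient for weight without age therefore answers a mixed question: the effect of being heavier for one's age, plus the effect of being older and taller. The plan's interest is in the first.

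The screening rule makes this harder to put right. Suppose OSA depends on adiposity for age and age has no effect of its own. Age is then unrelated to OSA univariately and would pass a 5% screen about 5% of the time, even if the team did add it to the candidates. Yet this is a case in which raw weight needs age beside it to recover the adiposity effect.

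At stake is the interpretation of the obesity odds ratio, a main secondary result. The outcome regressions share the gap: blood pressure and metabolic measures may also vary with age and sex, and body mass index is the only adjuster given as an example.

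**Working it through.** **The plan's own figure.** With p = 34/243 = 0.140 and half-width 0.025, n = 1.96² × p(1−p)/0.025² = 739.7, so 740 is reproduced. At 14% this gives about 104 cases. No power or effect size is stated for the risk-factor model.

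**Inputs**
- From the documents: ages 12-16, equal numbers per grade, N = 740, prevalence 14.0%.
- Assumed: age uniform from 12.0 to just under 17.0, so its variance is V = 5²/12 = 25/12; mean weight gain s (kg per year); within-age SD of weight, SDw (kg); adiposity log odds ratio b per within-age SD; independent age effect g (log-odds per year). The documents give none of the last four.

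**Model.** Weight = SDw × (adiposity for age) + s × age. For weight fitted alone, the linear approximation to the ratio of its coefficient to the within-age effect is

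ratio = (SDw² + g·s·V·SDw/b) / (SDw² + s²·V).

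**No independent age effect (g = 0)**
- s = 4, SDw = 10: 100/(100 + 16 × 25/12) = 100/133.3 = 0.75.
- s = 6, SDw = 8: 64/(64 + 75) = 0.46.
- s = 2, SDw = 12: 144/(144 + 8.33) = 0.945.

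**With an age effect (s = 4, SDw = 10, b = 0.4)**

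| g per year | formula | simulated logistic fit (n = 200,000) |
|---|---|---|
| −0.15 | (100 − 31.25)/133.3 = 0.52 | 0.49 |
| 0 | 0.75 | 0.75 |
| +0.15 | (100 + 31.25)/133.3 = 0.98 | 0.99 |
| +0.30 | (100 + 62.5)/133.3 = 1.22 | 1.22 |

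The ratio equals 1 when g = b·s/SDw = 0.4 × 4/10 = 0.16. The crossing point moves with the inputs: for b = 0.7 it is 0.7 × 4/10 = 0.28.

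**Waist, g = 0, same formula**
- 1.5 cm per year, SD 9 cm: 81/(81 + 4.69) = 0.945.
- 2 cm per year, SD 7 cm: 49/(49 + 8.33) = 0.855.
- 1 cm per year, SD 11 cm: 121/(121 + 2.08) = 0.983.

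The attenuation is thus about 2-15%.

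**What the alternatives recover.** When height is ignored, either adding age to weight or using an age-standardised score returns the ratio to about 1.0. If height makes up 25% of the within-age variance of weight (assumed), weight plus age recovers only about 0.85, while the z score stays near 1.0. Adding age alone is therefore the weaker repair. The z score recovers the effect partly by construction, because the simulated OSA risk depends on adiposity for age.

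**Power at N = 740** (simulated, 600 replicates; b = 0.3, s = 4, SDw = 10). With g = 0: weight alone 69%, weight plus age 80%, z score 80%. With g = +0.15: 93%, 82% and 81%. The 93% is not a gain, since the test is then partly of age. Monte Carlo error for the 69% is about 1.96 × √(0.69 × 0.31/600), or 4 percentage points.

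No calculation was made for the outcome regressions; that part rests on reasoning only.

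**The case against.** A reader might infer that the obesity effect will be diluted or understated, pointing to the background statement that childhood OSA tends to have remitted by adolescence. The documents do not support that. The passage contrasts childhood with adolescence, to argue for studying them separately; it gives no slope within 12-16 years. It also says that many adolescent cases are new, and the section on why adolescents are studied says developmental changes predispose to OSA. A positive age effect removes or reverses the dilution, as the table shows.

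A reader might also infer that the plan rules age out. It does not. Both covariate lists are open, and the Abstract speaks of demographic variables in general. This is a failure to commit to age, not an exclusion of it. Nor does the text say whether waist or body mass index would enter raw or as z scores; only body weight is necessarily raw, because no z score is planned for it. Sex is already a logistic candidate.

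The calculation fits weight alone, whereas the planned model may also hold waist, neck and sex, so the ratios describe the univariate step and need not carry over to the final model. Body weight can also be reported as a plain predictor, since the stated aim is to identify possible risk factors.

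These points limit the claim about direction and size. They do not answer the central one: the named adiposity measure carries growth, a better one is already derived, and the selection rule does not protect the age term.

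**Conclusion.** The point holds as a weakness of specification and method in secondary analyses. As written, the body-weight coefficient mixes adiposity with age and growth. Its bias has no known sign, because the age effect within 12-16 years is unknown. Under the assumed 4 kg per year and SD of 10 kg, with b = 0.4 where age has an effect, the ratio to the within-age effect runs from 0.49 to 1.22 for age effects of −0.15 to +0.30 log-odds per year, with 0.75 at zero. All growth and effect inputs are assumptions. The issue is mainly about weight; for waist it is small and the form of entry is unstated. For the outcome regressions, naming age and sex is sound practice, but the size of any confounding was not estimated. The primary prevalence estimate and the sample size of 740 stand.

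**What to change.** In Statistical Analysis:
- Replace body weight with BMI z score among the logistic candidates, and state that waist enters as its z score.
- Force age (or school grade) and sex into the multivariable logistic model whatever their univariate p values. Age is still needed alongside z scores, because neck circumference has none.
- In every multiple linear regression of cardiovascular, metabolic and cognitive outcomes on OAHI, include age and sex together with BMI as a z score.

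The cost is wording only. Age, sex, height and weight are already recorded and both z scores already derived, so no data collection, sample size or timetable changes.

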(3) There is accumulating evidence of 2 types of childhood OSA, namely one associated with lymphoid enlargement in the absence of obesity, and the other being primarily associated with obesity. [10] This classification of childhood OSA allows better distinction between patients. Evidence also suggests that genetic susceptibility of OSA has both obesity-dependent and obesity-independent components, thus emphasizing the importance of segregating obese and non-obese subjects in OSA research. [11] The OSA subtypes are distinct entities. Former is the classical childhood OSA and the latter being more akin to adulthood OSA where obesity plays an important role. As obesity is becoming more common among adolescents, [12] we can expect to see an increasing prevalence of OSA in this age group. Furthermore, research in this area may provide the important answer as to whether adulthood OSA begins from adolescence.

Relevance, significance and value of the study

With the obesity epidemic, the prevalence of OSA in adolescents will be expected to increase further. Taking into account the association between OSA and clinically important short and long term complications, our proposed study is highly relevant and will yield vital information on disease burden. Our study will also form a platform from which repeated measurements can be made to assess time trends and to answer the important question of whether adulthood OSA takes its origin from adolescence. This study, with both significant academic and clinical value will invariably enrich the scanty scientific literature on adolescent OSA. It will also build on our internationally recognised track record on OSA research.

(a) Background of research

Why study OSA?

The prevalence of childhood OSA is quoted to be around 1 to 5%. [13] However in studies that utilized parental report with additional diagnostic testing, the prevalence is as high as 12-24%. [13] The variation in reported prevalence can be explained by the use of different methodologies and diagnostic cut-offs. In Hong Kong, our research group has completed an OSA prevalence study in community-based children aged 5 to 13 years. We used a two-phase strategy, namely questionnaire screening followed by overnight sleep study and we found a prevalence rate of 3-

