It is a cross-sectional, population-based study. Subjects who are found to meet all the inclusion and none of the exclusion criteria will be recruited. They will complete a set of sleep-related questionnaires, undergo anthropometric measurements, home polysomnographic (PSG) monitoring, attention assessment and phenotyping of their metabolic and cardiovascular risk.

Pilot Data and Sample Size Estimation

We have previously established a school-based cohort in 2003-2005 which included children aged between 6 and 13 years to determine the prevalence of OSA. [1] We then conducted a 4-year follow-up for a subgroup of the cohort was carried out. [25] At follow-up, the subjects were aged between 10 and 17 years. A total of 243 teenagers returned for the follow-up visit. The prevalence of OSA defined by different cut-offs and the minimum sample size required to detect corresponding prevalence with various levels of precision are presented in table 1. On further analysis those who returned for the 4-year follow-up had higher baseline OSA severity compared to the rest of the cohort [OAHl: 1.0 (0.1–2.5) c.f. 0.6 (0–2.0), $p=0.007$], therefore the calculated prevalence is likely an over-estimation. Nonetheless, using the proposed sample size would provide adequate power should the genuine population prevalence is lower than the calculated one.

Table 1. Minimum sample size required to detect the prevalence of OSA defined by various cut-offs with different levels of precision.

	OAHl $\geq 5/h$	OAHl $\geq 1/h$	OAHl $\geq 1/h$ + habitual snoring (ICSD criteria)
No. of cases	34/243	120/243	31/243
Prevalence	0.140	0.494	0.128
Precision			

	Minimum sample size required		
0.01	4623	9603	4276
0.015	2055	4268	1900
0.02	1156	2401	1069
0.025	740	1536	684
0.03	514	1067	475
0.04	289	600	267
0.05	185	384	171

In the current settings with limited budget allocation, our research team is capable of recruiting 740 adolescents to detect a prevalence of 14.0% with a precision of 2.5% (i.e. 95%CI: 11.5–16.5%) for the OAH1 \geq 5/h cutoff. The sample size can also ensure a precision of <4% for the OAH1 \geq 1/h cut-off and a precision of <2.5% for the ICSD criteria. [31] The sample size would also provide >99% power to detect the differences between the estimated prevalence of OSA in adolescents and the published prevalence of OSA in primary school children [1] no matter which cut-off is being used.

Sampling Frame

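### Letting univariate p<0.05 decide which risk factors enter the logistic model can drop negatively confounded factors and tends to bias the odds ratios that are kept

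*Combined protocol and SAP*

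**What the plan says.** The Statistical Analysis section states the aim: "Logistic regression analysis will be used to identify possible risk factors of OSA in adolescents". The candidates are introduced as factors that may be relevant: "male sex, body weight, waist circumference, neck circumference, tonsil size, modified Mallampati score and chronotype". The procedure has two steps: "All these factors will be first assessed in univariate analysis", and then "Those found to be significantly associated with OSA in univariate analysis will be assessed in multivariate model". One significance level, p<0.05, is given for all analyses. The section does not keep any factor regardless of its univariate result, set a looser entry threshold, or describe shrinkage or validation.

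The same section handles the linear models of health outcomes differently. Those adjust for confounders such as body mass index, and no univariate screen is mentioned. The Abstract lists logistic models of OSA against demographic and clinical variables among the secondary outcomes, so this is declared work.

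Key Issues (3) describes two forms of childhood OSA, "one associated with lymphoid enlargement in the absence of obesity, and the other being primarily associated with obesity". The background section on the two types adds that the obese form shows only mild lymphoid enlargement.

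**The concern.** A univariate test measures a factor's own effect plus whatever it carries from correlated factors. If two genuine risk factors are negatively correlated, each partly hides the other, and a screen can remove one before the adjustment that would reveal it. Separately, a weak factor that has to reach p<0.05 to be carried forward does so more often in samples where its estimate is high by chance. The p value and confidence interval then reported take no account of that selection.

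The two-phenotype description makes tonsil size and adiposity a natural pair to worry about. What is at stake is the secondary risk-factor analysis: which factors appear in the adjusted table, and how large their odds ratios look.

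**Working it through.** **The plan's own figure.** Pilot Data and Sample Size Estimation gives 740 for a prevalence of 14.0% with precision 2.5%. With n = z²p(1−p)/d², this is 1.96² × 0.14 × 0.86 / 0.025² = 740. It reproduces. It concerns the prevalence estimate; the documents give no figure for the risk-factor model.

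**Inputs.** From the documents: n=740, prevalence 14%, seven candidates, threshold 0.05 (taken as two-sided). Assumed, because the documents give none: tonsil size OR 1.3 per SD, one adiposity measure OR 1.8 per SD, and their correlation r, which is varied. Clustering by school is not modelled.

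**Approximation by hand.** The univariate log odds ratio for tonsil size is roughly ln(1.3) + r × ln(1.8) = 0.262 + 0.588r. Its standard error is about 1/√(740 × 0.14 × 0.86) = 1/√89.1 = 0.106.
- r = 0: 0.262, an apparent OR of 1.30.
- r = −0.2: 0.262 − 0.118 = 0.145, an apparent OR of 1.16. The chance of p<0.05 is about Φ(0.145/0.106 − 1.96) = Φ(−0.59) = 28%.
- r = +0.2: 0.262 + 0.118 = 0.380, an apparent OR of 1.46.

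**Simulation.** Logistic regression, 2,000 or more samples per setting. Monte Carlo error on a rate is about 1 percentage point, and repeat runs agreed to within about 2.

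| Correlation | Tonsil size passes the screen | Significant when both are always fitted |
|---|---|---|
| −0.4 | 6% | 59% |
| −0.2 | 27% | 67% |
| −0.1 | 45% | 66% |
| 0 | 66% | 67% |
| +0.1 | 80% | 64% |
| +0.2 | 93% | 65% |

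**Size of the retained odds ratio.** Mean adjusted tonsil OR among samples that pass:

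| True OR | r = 0 | r = −0.2 |
|---|---|---|
| 1.2 | 1.34 | 1.43 |
| 1.3 | 1.38 | 1.49 |
| 1.5 | 1.52 | 1.58 |

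For a true 1.3 this is an excess of 1.38/1.30 = 6% at r = 0 and 1.49/1.30 = 15% at r = −0.2. At r = −0.2, interval coverage among the passing samples is about 89%. The always-fitted model averages close to the true value with about 95% coverage. For adiposity the bias runs the other way: when tonsil size is screened out, the adiposity OR falls from about 1.81 to 1.73 at r = −0.2 and 1.63 at r = −0.4.

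**Can the data carry all the factors?** Expected cases = 740 × prevalence, divided by 7 candidates:
- 14.0% (OAHI ≥5/h): 104 cases, 14.8 per factor.
- 12.8% (ICSD criteria): 95 cases, 13.5 per factor.
- 49.4% (OAHI ≥1/h): 366 cases, 52 per factor.
- 5.8% and 3.8% (childhood rates in Key Issues (1)): 43 and 28 cases, 6.1 and 4.0 per factor.

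The low case matters because the sample-size section says of its pilot data: "therefore the calculated prevalence is likely an over-estimation". At 5% prevalence and r = 0, a true OR of 1.3 averages about 1.58 among samples that pass, so screening does not solve the problem of few events.

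**The case against.** **The masking depends on an unstated correlation.** A reader might infer from the two phenotypes that tonsil size will be dropped. The documents do not support that. They describe children who have OSA, whereas masking depends on the correlation in the whole sample. Two independent routes to OSA produce a negative correlation among cases with none in the population: a simulation with population correlation 0 and 14% prevalence gave −0.17 and −0.30 among cases and 0.00 among non-cases, for assumed log-odds slopes of 1.0 and 1.5 per SD. At zero correlation the screen costs almost nothing in detection, and at positive correlation it passes tonsil size more often than the full model finds it significant. This objection stands and makes the point conditional.

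**Inflation is not universal.** A reader might infer that every surviving odds ratio is inflated. It is negligible for a strong uncorrelated factor and reversed for adiposity when tonsil size is lost. At zero correlation it is ordinary selection on significance: a true 1.2 averages 1.34 after passing the screen and 1.35 among significant full-model results. The full model's gain there comes from reporting every estimate. This also stands.

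**Few cases may make a full model hard to fit.** At 4 to 6 cases per factor this is a fair warning. It argues for a smaller prespecified set or a penalised fit, and gives no support to univariate screening.

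**The analysis is exploratory.** It is secondary and cautiously worded, and nothing says that a non-significant factor will be declared irrelevant. That limits the severity. The screening rule still fixes what is adjusted for.

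**Conclusion.** The point holds in a conditional form. The screen can drop negatively confounded factors, with tonsil size a plausible but undocumented example, and it tends to bias the retained odds ratios, usually upward for weak or moderate factors. Under the assumed effect sizes, the loss of detection ranges from nearly nothing at zero correlation to about 40 percentage points at −0.2 (67 − 27). These figures illustrate the mechanism and do not predict this study's results, since both the effect sizes and the correlation are assumptions.

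The case for change does not depend on knowing the correlation: the always-fitted model gave nearly unbiased estimates and about 95% coverage at 14% prevalence, whichever sign was assumed. The change is worth making before analysis. It concerns a secondary analysis only.

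**What to change.** Replace the screening sentence with wording such as: *The listed factors (sex, one prespecified adiposity measure, neck circumference, tonsil size, modified Mallampati score, chronotype) will be entered together in one logistic model regardless of univariate significance, and all estimates will be reported; univariate results are descriptive.*

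This replaces body weight and waist circumference with a single adiposity measure, to be named in advance, because the two overlap. Neck circumference stays and will still share some information with that measure.

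Add a fallback: *If the number of cases is small, a smaller prespecified set of factors or a penalised (for example Firth) fit will be used.* The plan should state the case count that triggers it and name the reduced set beforehand.

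No new data, visits or participants are needed. The cost is slightly wider confidence intervals for some factors at the planned prevalence; with few cases the intervals will be wide under any method. Allowing for school clustering is a separate question and is not part of this change.
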